**The Effect of Using Two Different Suturing
Techniques on Free Gingival Marginal Stability
after Esthetic Crown Lengthening for Treatment
of Gummy Smile
(Randomized Clinical Trial)**

Methodology

Document date: 3 /1/2020

Sample selection and assignment:

Thirty patients (26 females, 4 males), who were candidates for esthetic crown lengthening, participated in this prospective clinical trial.

The subject was recruited consecutively from the outpatient clinic of Oral Medicine, Periodontology, oral Diagnosis and Radiology Department, Faculty of Dentistry, Ain Shams University and faculty of dental medicine, Misr international University. The purpose of the study was explained to all patients and an informed consent was signed before the conduction of the study. The proposal was presented to the faculty of Dentistry Ain Shams University Research Ethics committee and was approved before starting the research ()

Patient selection:

Inclusion Criteria:

1. Patients complaining from gummy smile (altered passive eruption)
2. Age range (21-40) years.

3. Bone level is 2 mm or less from the cemento enamel junction
4. Teeth included were free from any periodontal destruction
5. Good compliance with the plaque control instructions following initial therapy.
6. Availability for follow up and maintenance program.

Exclusion criteria:

1. Presence of systemic diseases which could influence the outcome of the therapy (*American society of anesthesiologists I, ASA I*).
2. Patient suffering from periodontitis stage 4 grade C.
3. Presence of smoking habit.
4. Presence of occlusal interferences.
5. Pregnant females and lactating females. .
6. Vulnerable groups of patients (handicapped, mentally retarded and prisoners).
7. Restored teeth.

Grouping Criteria:

The study consisted of two groups the number of patient was determined by sample size calculation through G power analysis (15 patients). Patients were randomly selected using computer generated randomization (www.randomizer.org).

Group 1 (15 patients) (Periosteal suture) :

Esthetic crown lengthening procedure: internal bevel, sulcular and interdental incisions, flap elevation, bone removal then External vertical mattress suture was done (periosteal suture).

Group 2 (15 patients) (Figure of eight suture) :

Esthetic crown lengthening procedure: internal bevel, sulcular and interdental incisions, flap elevation, bone removal then modified interrupted suture was done (Figure of eight suture).

III- Assessments:

1-Clinical parameters:

For the selected sites, the following clinical parameters were assessed preoperative (baseline) 3 and 6 months after surgical procedure.

1. Plaque index *Silness and Löe 1964*
2. Gingival Index *Löe and Silness 1963.*
3. Probing depth (PD) *Glavind and Loe, 1967*
4. Length of Attached gingiva

2-Esthetic outcome evaluation:

The following parameters were assessed 1, 3 and 6 months after surgical procedure:

- Level of the gingival margin (GM) through measurement of the crown length from the reference point in the surgical stent to the gingival margin (*Deas et al., 2004*).
- Marginal tissue contour (MTC) using root coverage esthetic score (RES) system (*Cairo et al. 2009*): Zero points = irregular gingival margin (does not follow the CEJ); 1 point =proper marginal contour/scalloped gingival margin (follows the CEJ).

- Papillary fill using classification of papillary fill (*Jemt 1997*) which it's score is as follows:
 - PIS1: entire papilla missing, lack of convexity
 - PIS 2: fills less than the interdental space, slight convexity.
 - PIS 3: fills more than half the interdental space but no complete fill
 - PIS 4: papilla fills the entire space, harmonic gingival contour
 - PIS 5: hyperplastic papilla covering too much tooth structure, irregular tissue contour
- Patient satisfaction prior surgery and 6 months post-surgery (*Silva et al., 2015*).

Patient satisfaction criteria

Prior to surgery

- How would the patient rate the gun shown when smiling, size of the upper teeth, the length of upper teeth and the width of it (way too little, too little, about enough and too much way too much)

After surgery

- Is the patient satisfied with the gingival display during talking and smiling, teeth display during

Material and Method

talking and smiling (not at all, slightly, somewhat, very and extremely).

- How was the procedure experience (much worse, worse, same as I thought, better and much better).

Presurgical therapy:

- Full Conventional periodontal treatment including supra, subgingival scaling and root planning were performed using hand scalers and curettes.
- Oral hygiene instructions(regular brushing 3 times/day, flossing and using mouthwash) were repeated until patients had achieved a proper level of oral hygiene where plaque index (PI) ≤ 1 .
- Teeth were examined for caries, periapical infection and restorative procedures in order to be treated.
- Assessment parameters were recorded prior to surgery using UNC-15* manual probe (Hu Friedy)
- Alginate impressions were made 4 weeks following initial therapy of each maxillary arch to fabricate customized probing stents. Full-arch probing stents were made on stone casts Stents were trimmed to the height of contour, and

* PCPUNC15 Single-ended, color-coded probe. ergonomic handle. University of North Carolina, Hu Friedy, USA.

Material and Method

grooves were placed at sites to be measured with a narrow fissure bur to act as reference points for clinical parameters assessment.

(IV) Surgical procedures

Group (1)

- 1) Anesthesia (Articaine HCL 4% containing epinephrine at a concentration of 1:100,000)[†] was administrated at the selected teeth.
- 2) The tooth width to length ratio was determined according to the golden proportions (RED: The successive width proportion, when viewed from the facial aspect, should remain constant as we move posteriorly from the midline) (***Ward 2001***)
- 3) Bone sounding was done(patient was given anesthesia probing until the bone level was done using UNC-15[‡] manual probe) to determine the bone position in relevance to the CEJ position then bleeding points were done to determine the amount of the gingival tissue that was removed

[†] Artinibsa 4%cartouches de 1.8ml ,inibisa dental.

[‡] PCPUNC15 Single-ended, color-coded probe. ergonomic handle. University of North Carolina, Hu Friedy, USA.

Material and Method

- 4) Primary submarginal incision, secondary intrasulcular then tertiary incision at the papillary area were done using the surgical blade (15c)[§]
- 5) Full thickness flap reflection at the crestal bone area using mucoperiosteal ** elevator was done, while at the papillary area partial thickness flap using the surgical blade (15c)^{††} was done.
- 6) After flap reflection the supracrestal soft tissue were removed using surgical curette^{‡‡} (universal curette 2R/2L,4R/4L)
- 7) Ostectomy 3mm from the cemento enamel junction were performed using end cutting burs^{§§}. Root surfaces were scaled to remove remnants of supracrestal connective tissue fibers.
- 8) Flap was repositioned by external vertical mattress (periosteal suture) suturing technique using resorbable 5-0 vicryl sutures^{***}

[§] Trinon sterile scalpel Blades ,lot0483,Germany

^{**} Buser Periosteal handle #6, Hu- Friedy, USA.

^{††} Trinon sterile scalpel Blades ,lot0483,Germany

^{‡‡} Universal Curettes(2R/2L),(4R/4L), Hu-Friedy ,USA

^{§§} Midwest operative Carbide burs,FG,End cutting, #957,1.0mm diameter,3.7mm length,10/Pkg,Dentsply Midwest,Patterson item#493-0079,Mfg item#:389278.

^{***} Assut Sutures, Absorbable (PGA) 5-0 USP, braided violet coated 3/8 rev.cutt.17mm, AM trading.

Fig (3): Showing diagram for the periosteal suture

Group (2)

- 1) Anesthesia (Articaine HCL 4% containing epinephrine at a concentration of 1:100,000)^{†††} was administrated at the selected teeth.
- 2) The tooth width to length ratio was determined according to the golden proportions (RED).
- 3) Bone sounding was done to determine the bone position to in relevance to the CEJ position then bleeding points were done to determine the amount of the gingival tissue that was removed
- 4) Primary submarginal incision, secondary intrasulcular then tertiary incision at the papillary area were done.
- 5) Full thickness flap reflection at the crestal bone area using mucoperiosteal^{‡‡‡} elevator was done, while at the papillary area partial thickness flap using the surgical blade (15c)^{§§§} was done.

^{†††} Artinibsa 4% cartouches de 1.8ml ,inibisa dental.

^{‡‡‡} Buser Periosteal handle #6, Hu- Friedy, USA.

^{§§§} Trimon sterile scalpel Blades ,lot0483,Germany

Material and Method

- 6) After flap reflection the supracrestal soft tissue were removed using surgical curette**** (universal curette 2R/2L,4R/4L)
- 7) Ostectomy 3mm from the cemento enamel junction were performed using end cutting burs††††. Root surfaces were scaled to remove remnants of supracrestal connective tissue fibers.
- 8) Flap was repositioned by modified interrupted (figure of 8 suture) suturing technique using resorbable 5-0 vicryl sutures††††.

[figure not shown]

Fig (4): Showing a diagram for the interrupted modified sutur

**** Universal Curettes(2R/2L),(4R/4L), Hu-Friedy ,USA

†††† Midwest operative Carbide burs,FG,End cutting, #957,1.0mm diameter,3.7mm length,10/Pkg,Dentsply Midwest,Patterson item#493-0079,Mfg item#:389278.

††† Assut Sutures, Absorbable (PGA) 5-0 USP, braided violet coated 3/8 rev.cutt.17mm, AM trading.

V-Postoperative care:

- All patients had received antibiotic for 1 week
(Augmentin 1 gm every 12 hours\$\$\$\$, metronidazole ***** 500gm every 12 hours) and analgesics(Brufen ††††† 400 every 8 hours) were prescribed for the patient and instructed to avoid brushing at the surgical site
- Patients were instructed to rinse twice daily with Tantum verde[■] mouth rinse or hot saline mouthwash and to avoid mechanical plaque removal at the site of surgery
- Sutures were removed after 2 week.
- Patients were instructed not to brush for 2 weeks and not to floss the surgical area for 4 weeks.
- After 15 days patient were instructed to use modified bass technique for tooth brushing (***Carranzaa 12th edition***)

\$\$\$\$ Augmentin 1gm,Medical union pharmaceuticals(MUP) Egypt under license from ,Glaxosmithkline

***** Flagyl 500 mg, sanafi Aventis Egypt under license of sanafi Aventis French.

††††† Brufen 400mg, Al kahira pharm. and chem.Ind.Co. under license from abbott laboratories

[■]Tantum Verde Mouthwash and Gargle(Benzydamine hydrochloride 0.15g): Bottle of 125 ml, Eipico Egypt under license of A.C.R Angelini Francesco.SpA.Italy

VI-Postoperative evaluation and assessment:

Monthly recall appointments were scheduled

- The follow up period included oral examination, plaque and calculus removal when necessary
- Clinical and esthetic parameters were evaluated and scored by a separate operator at 1, 3 and 6 months postoperative the patient satisfaction was evaluated 6 months post-operative only
- All data were statistically analyzed

VII-Statistical analysis:

Statistical analysis was then performed using a commercially available software program (SPSS 18; SPSS, Chicago, IL, USA).

Values were presented as mean, standard deviation (SD), median, range and confidence intervals. Data were explored for normality using Kolmogorov-Smirnov test of normality. For parametric data, Independent t test was used for 2 group's comparisons, while ANOVA test was used to compare different observations.

Material and Method

Plaque and gingival indices and most values of difference and percent change were non-parametric and were compared using Mann Whitney U test for intergroup comparisons, while Friedman test and Wilcoxon signed Rank test were used for intragroup comparisons

Qualitative data were expressed as frequencies and percentages and were compared using Chi square test

The level of significance was set at $P \leq 0.05$.

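### Patients come from two university clinics, but the plan describes no stratification by clinic and compares the suture groups without a clinic term

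*Combined protocol and SAP*

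**What the plan says.** Under Sample selection and assignment, the combined protocol and SAP reports "Thirty patients (26 females, 4 males), who were candidates for esthetic crown lengthening". It adds that "The subject was recruited consecutively from the outpatient clinic" and names two institutions: "Faculty of Dentistry, Ain Shams University and faculty of dental medicine, Misr international University". It does not give the number of patients from each.

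Under Grouping Criteria, assignment is covered by one sentence: "Patients were randomly selected using computer generated randomization (www.randomizer.org". The arms are "Group 1 (15 patients) (Periosteal suture" and "Group 2 (15 patients) (Figure of eight suture". The section does not mention stratification, blocking or the number of lists.

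The Surgical procedures section gives both groups the same steps up to suturing, but does not say who operated or at which institution. Section VI mentions one operator only, the separate person who scored the outcomes.

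Section VII compares the groups by independent t test, Mann-Whitney U test or chi-square test. None of these includes clinic or operator.

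**The concern.** Two institutions can differ in the patients they send, in oral hygiene before surgery and, if surgery was done at both, in the surgeon. The steps before suturing (bone sounding, bleeding points, submarginal incision, bone removal) are done by hand and could affect the gingival margin level.

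In a large trial, chance would spread the clinics evenly enough over the arms. With 15 per arm, one clinic can supply noticeably more of one suture group. If the clinics also differ in outcome, part of that difference appears in the suture comparison, and the planned tests cannot separate the two.

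**Working it through.** **Inputs from the document.** 30 patients, 15 per arm, two recruiting institutions, unadjusted between-group tests.

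**Assumptions, because the document gives no figures.** The smaller clinic supplies K = 8 to 12 of the 30 patients. Assignment ignores clinic. The clinics differ in outcome by 0.5 to 1 within-clinic SD.

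**The plan's own figure.** The document gives no figure for clinic balance. It cites "sample size calculation through G power analysis (15 patients", but with no effect size, SD or power, so the 15 cannot be reproduced. Solving backwards (two-sided 0.05, noncentral t), 15 per arm has 80% power for a difference of about 1.06 SD.

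**Step 1: chance of imbalance.** If x of the smaller clinic's K patients fall in Group 1, then P(x) = C(15, x) × C(15, K − x) / C(30, K), and the difference between arms is |2x − K|.

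Example for K = 10, where C(30, 10) = 30,045,015:
- A difference of 4 or more needs x ≤ 3 or x ≥ 7: 2 × (2,927,925 + 675,675 + 75,075 + 3,003) / 30,045,015 = 0.245.
- A difference of 6 or more needs x ≤ 2 or x ≥ 8: 2 × (675,675 + 75,075 + 3,003) / 30,045,015 = 0.050.

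| Patients from smaller clinic | P(difference ≥ 4) | P(difference ≥ 6) |
|---|---|---|
| 8 | 0.215 | 0.035 |
| 9 | 0.109 | 0.014 |
| 10 | 0.245 | 0.050 |
| 11 | 0.128 | 0.021 |
| 12 | 0.264 | 0.060 |

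Odd K allows only odd differences, so there the two columns mean 5 or more and 7 or more. That is why the values alternate. Over the assumed range the probabilities are 11 to 26% and 1.4 to 6%. Outside it, P(difference ≥ 4) is 4% for K = 5, 17% for K = 6 and 14% for K = 15.

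**Step 2: effect on the estimate.** Shift in the unadjusted mean difference = clinic effect × (difference in counts / 15).
- 4 patients: 0.5 × 4/15 = 0.13 SD; 1 × 4/15 = 0.27 SD.
- 6 patients: 0.5 × 6/15 = 0.20 SD; 1 × 6/15 = 0.40 SD.

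**Step 3: comparison with random error.** The standard error of a difference between two means of 15 is √(2/15) = 0.365 SD. A 4-patient difference therefore moves the estimate by 0.13/0.365 = 0.36 to 0.27/0.365 = 0.74 of a standard error.

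**Step 4: what adjustment gains or loses.** In simulation with K = 10, adding a two-level clinic factor to the comparison changes the standard error as follows:
- no clinic effect: about 2% larger;
- clinic effect 0.5 SD: about 1% smaller;
- clinic effect 1 SD: about 8% smaller.

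**Step 5: what stratification would have done.** Permuted blocks within clinic cap the difference in each clinic at 1 patient (block size 2) or 2 patients (block size 4). For a clinic effect of 0.5 SD the largest shift is then 0.5 × 1/15 = 0.03 SD or 0.5 × 2/15 = 0.07 SD.

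**The case against.** Four points weigh on the other side.

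1. **The number of lists is not stated.** A reader might infer that all patients were assigned from one common unstratified list. The document does not say so: separate lists per clinic are neither described nor excluded. This stands, and the probabilities above apply only if assignment ignored clinic. It does not rescue the analysis, which leaves clinic out either way.

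2. **No operator difference is shown.** A reader might infer two surgical teams from two recruiting institutions. Recruiting at two places does not establish operating at two places, and one surgeon may have treated everyone. This also stands. Differences between the clinics' patients would remain possible.

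3. **The clinic effect may be small.** Both groups follow the same surgical steps with the same instruments. The margin is measured from a stent reference point, and a separate operator scores it. Where the analysis uses change between postoperative visits, a clinic difference in where the margin was first placed largely cancels. This makes 0.5 to 1 SD less plausible, though it does not exclude a clinic difference in margin level or healing. No document figure supports or refutes the assumed range.

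4. **Chance imbalance is not bias.** A reader might conclude that the suture comparison is biased. Under valid randomisation the imbalance averages to zero over repetitions, and the standard error allows for it. This stands. What remains is conditional: a reader of this one trial faces the split it actually has, and the document does not report that split.

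**Conclusion.** The point holds as a minor one. Two clinics supplied the patients, no stratification by clinic is described, and the planned between-group tests contain no clinic term.

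Given unstratified assignment and 8 to 12 patients from the smaller clinic, an imbalance of 4 or more has a probability of 11 to 26%. It would shift this trial's estimate by 0.13 to 0.27 SD if the clinics differ by 0.5 to 1 SD. That is below one standard error (about 0.37 SD) and well below the roughly 1.06 SD that 15 per arm can detect with 80% power. The 0.40 SD shift needs both a 6-patient imbalance, with probability 6% or less, and a full 1 SD clinic effect.

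Clinic sizes and clinic effect are assumptions. A table of clinic by arm would replace the first, and a clinic-adjusted analysis would estimate the second.

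**What to change.** 1. State how the sequence was generated: one list or one per clinic, and any blocking.
2. Report the number of patients by clinic and arm, and by operator and arm if more than one surgeon operated.
3. Compare gingival margin level between groups with a linear model containing suture group and clinic. Where the plan uses Mann-Whitney, which takes no covariate, use the clinic-stratified rank test (van Elteren).
4. If any assignment is still to be made, use randomly permuted blocks within clinic. The document reports in the past tense that all 30 patients took part, so this step is probably no longer available.

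No extra patients or visits are needed. The adjusted model uses one degree of freedom and loses about 2% in precision if the clinics do not differ. Blocks within clinic, if still possible, could leave the arms one or two patients away from 15 when a block is incomplete.

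### The esthetic schedule gives papillary fill no pre-surgical score, so an incomplete papilla at 6 months cannot be attributed to surgery

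*Combined protocol and SAP*

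**What the plan says.** Section III (Assessments) sets two schedules. Under 1-Clinical parameters, "the following clinical parameters were assessed preoperative (baseline) 3 and 6 months after surgical procedure"; the list is plaque index, gingival index, probing depth and attached gingiva. Under 2-Esthetic outcome evaluation, "The following parameters were assessed 1, 3 and 6 months after surgical procedure". One item there is "Papillary fill using classification of papillary fill", scored on five levels (PIS 1 to 5). In the same list, satisfaction has its own times: "Patient satisfaction prior surgery and 6 months post-surgery".

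Presurgical therapy adds one general sentence: "Assessment parameters were recorded prior to surgery using UNC-15* manual probe". It does not say which parameters are meant.

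Section VI (Postoperative evaluation and assessment) says: "Clinical and esthetic parameters were evaluated and scored by a separate operator at 1, 3 and 6 months postoperative".

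**The concern.** Each PIS level describes the papilla at one visit. For example, "PIS 3: fills more than half the interdental space but no complete fill" is a state, not a change. In both groups, steps 4 and 5 of the surgical procedures include an incision in the papillary area and a partial-thickness flap there, so loss of papilla is a plausible consequence of the operation and a natural thing to compare between sutures. If the score is first taken at 1 month, a PIS 3 at 6 months looks the same whether the papilla was full before surgery or was already at PIS 3.

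Two things are at stake. Within a patient, incomplete fill cannot be attributed to surgery. Between groups, a chance difference in starting fill can be neither seen nor adjusted for, and with 15 patients per group such differences are not rare unless incomplete fill is uncommon at entry. Section VII also plans comparisons of differences and percent changes without naming the reference visit; the esthetic schedule offers no pre-surgical reference for papillary fill.

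**Working it through.** **Reading the schedule.** No figure in the plan bears on this point, so there is none to reproduce.

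| Item | Pre-surgical reading stated? | Where |
|---|---|---|
| Clinical parameters | Yes | III, 1-Clinical parameters |
| Patient satisfaction | Yes | III, 2-Esthetic outcome evaluation |
| Papillary fill | No; 1, 3 and 6 months only | III, 2-Esthetic outcome evaluation |
| Unnamed assessment parameters | Yes, with a manual probe | Presurgical therapy |

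Where a pre-surgical reading was intended, the assessment lists generally say so. The probe sentence is the only text that could supply one for papillary fill. It neither names that score nor fits it closely, because PIS is defined by how far the papilla fills the space and by its contour, not by a probe reading.

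**Does eligibility make the baseline known?** The inclusion criteria require teeth free of periodontal destruction. That makes prior papilla loss less likely, but complete fill (PIS 4) is not an entry condition.

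**How often would chance imbalance arise?** Inputs: 15 patients per group (Grouping Criteria), and a proportion p of patients with incomplete fill before surgery. The documents do not give p, so it is assumed over a range. Each patient counts once as complete or incomplete. With X and Y independent and each Binomial(15, p), the chance that the groups differ by 3 or more patients is

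P(|X − Y| ≥ 3) = 1 − P(|X − Y| ≤ 2).

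At p = 5%, the probabilities of a difference of 0, 1 and 2 patients are 0.368, 0.446 and 0.149. Their sum is 0.962 after rounding, which leaves 0.038. Over the range:

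| Assumed p | P(difference of 3 or more patients) |
|---|---|
| 2% | 0.005 |
| 5% | 0.038 |
| 10% | 0.121 |
| 20% | 0.249 |
| 30% | 0.318 |

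**What could such an imbalance do alone?** Suppose a 3-patient difference carried over unchanged to 6 months and was tested with the planned chi-square test, uncorrected:

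- 0 of 15 against 3 of 15: χ² = 30 × (0×12 − 3×15)² / (15 × 15 × 3 × 27) = 60,750 / 18,225 = 3.33, p = 0.068.
- 3 of 15 against 6 of 15: χ² = 30 × (3×9 − 6×12)² / (15 × 15 × 9 × 21) = 60,750 / 42,525 = 1.43, p = 0.23.

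Neither reaches 0.05. An imbalance of this size would not by itself produce a significant result in these cases, though it could add to or mask a real difference.

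**The case against.** The best reply is that the baseline may exist. The Presurgical therapy sentence is not restricted to the clinical list, and section III is the parent heading of both lists, so its wording could be meant to cover papillary fill. This stands in part: a reader might infer that no pre-surgical score was taken, and the documents do not establish that. What they show is a specific schedule without the score and a general sentence that may or may not include it.

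A reader might also take section VI as confirming the omission. It does not. That section concerns postoperative visits, and it likewise leaves out the pre-surgical readings that section III gives to the clinical parameters and to satisfaction.

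Next, randomisation. The comparison of postoperative scores between groups is unbiased on average, and the type I error rate already allows for chance baseline imbalance. This stands in full, so the claim that the comparison is biased would be wrong. What is lost is attribution within a patient and the means to adjust.

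On size, the participants are aged 21 to 40, have altered passive eruption and have teeth without periodontal destruction, so the prevalence of incomplete fill may lie at the low end, where serious imbalance is uncommon. This is fair, and it is why the range above starts at 2%.

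Finally, one might extend the point to marginal tissue contour, which shares the schedule. The case is not made there: both procedures cut a new margin, so it is unclear what a pre-surgical contour score would add to the suture comparison. Nor can a gain in effective sample size from adjustment be quoted, because the documents give no baseline-outcome correlation and the usual variance formula does not suit a five-level ordinal score.

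**Conclusion.** The point holds for papillary fill, as a minor and cheaply remedied gap. On the specific schedule there is no pre-surgical PIS, and the general probe sentence does not clearly supply one. As scheduled, the data can compare postoperative papillary status between the sutures, but cannot show how much papilla was lost through surgery.

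The illustrative size is a chance of about 4%, 12% or 25% of a baseline difference of 3 or more patients, at assumed prevalences of 5%, 10% or 20%. These figures depend wholly on the assumed prevalence. The attribution problem does not depend on that figure; it needs only that some patients could enter with incomplete fill, which eligibility does not exclude. The conclusion does not extend to bias in the group comparison or to marginal contour.

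**What to change.** 1. Reconcile the esthetic schedule in section III with the Presurgical therapy sentence, and state whether papillary fill was scored before surgery.
2. Score papillary fill (PIS) at the existing pre-surgical recording.
3. Name the analysis, choosing one of two. The first compares the groups on worsening from baseline, defined as a fall to PIS 3 or below from a higher level, or a further fall within PIS 1 to 3. A change from PIS 5 to PIS 4 does not count, since PIS 5 is hyperplastic and PIS 4 is complete fill. The second compares 6-month scores adjusted for baseline with an ordinal method.
4. The document is written in the past tense. If surgery is complete and no pre-surgical score exists, report papillary fill as postoperative status and do not describe it as papilla loss.

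The cost is a few minutes of scoring per patient, with no new visit, staff or procedure, and no change to the 15 per group.

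### The definitions of papillary fill levels 2 and 3 overlap, and the plan names no test for a score whose highest number is not its best result

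*Combined protocol and SAP*

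**What the plan says.** Section III (Assessments), under Esthetic outcome evaluation, lists papillary fill among the parameters introduced by "The following parameters were assessed 1, 3 and 6 months after surgical procedure". It has five levels:

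- Level 1 is an absent papilla without convexity.
- Level 2, the first of the two levels at issue, is worded "PIS 2: fills less than the interdental space, slight convexity".
- Level 3, the second of them, is worded "PIS 3: fills more than half the interdental space but no complete fill".
- Level 4 is complete fill with a harmonious outline, the favourable state.
- Level 5, which carries the highest number, is worded "PIS 5: hyperplastic papilla covering too much tooth structure, irregular tissue contour".

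There is no tie-break between adjacent levels and no statement of which direction is favourable. Section VI says that a separate operator did the scoring and describes no calibration.

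Section VII (Statistical analysis) presents values as means, SDs and medians, among other summaries. It says that the plaque and gingival indices and most change values "were non-parametric and were compared using Mann Whitney U test for intergroup comparisons", and it assigns chi-square to qualitative data. Papillary fill is named under neither.

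**The concern.** There are two separate problems.

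The first is measurement. If one papilla satisfies two levels, the recorded level depends on the scorer's habit and not only on the tissue. That adds noise to the comparison of the two suture groups. It also makes the tabulated frequencies of levels 2 and 3 hard to interpret.

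The second is analysis. The number rises with the amount of papillary tissue, but esthetic quality peaks at 4 and falls at 5. An analysis that averages or ranks the raw number credits overgrowth as better than ideal fill, and lets overgrowth and underfill cancel. An analysis of unordered categories does neither. The plan leaves both routes open for this outcome, so the result could depend on a choice that the plan does not make.

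**Working it through.** **Overlap.** The plan states no figure to reproduce. The inputs are the level 2 and level 3 definitions in section III. Let f be the fraction of the interdental space filled and read only the fill wording.

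- Level 2 as written: 0 < f < 1 (f = 0 is level 1).
- Level 3: 0.5 < f < 1.
- Intersection: 0.5 < f < 1, which is the whole of level 3.

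| f | Level 2 as written | Level 3 | Level 2 if less than half | Level 2 if half or less |
|---|---|---|---|---|
| 0.25 | yes | no | yes | yes |
| 0.50 | yes | no | no | yes |
| 0.51 | yes | yes | no | no |
| 0.75 | yes | yes | no | no |
| 0.99 | yes | yes | no | no |

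The convexity remark in level 2 does not separate the two, because level 3 has no convexity criterion. Inserting only the word half would remove the overlap but leave f = 0.50 in no level. Half or less closes both.

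**Order.** The group size of 15 is from Grouping Criteria. The counts below are invented, with one score per patient. That is an assumption, because the plan does not state the unit for this score.

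*Example 1.* Group A has 12 at level 4 and 3 at level 5. Group B has 12 at level 4 and 3 at level 3. Ideal fill is 12/15 = 80% in both.

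- Means: (12×4 + 3×5)/15 = 4.2 and (12×4 + 3×3)/15 = 3.8.
- Mann-Whitney U for A: ½×12×12 (ties at 4) + 12×3 (4 over 3) + 3×12 (5 over 4) + 3×3 (5 over 3) = 72 + 36 + 36 + 9 = 153, out of 225.
- Asymptotic p = 0.017. With 24 of the 30 values tied, the exact permutation value, p = 0.035, is the safer one.

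Ranks on the raw number therefore favour the group with overgrowth.

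*Example 2.* Group A has 3 at level 3, 9 at level 4 and 3 at level 5. Group B has 15 at level 4.

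- Means: (9 + 36 + 15)/15 = 4.0 and 4.0. U = 112.5 = 225/2, p = 1.0.
- Ideal fill: 9/15 = 60% against 15/15 = 100%, Fisher's exact p = 0.017.
- Chi-square on the three occupied levels: expected counts are 1.5, 12 and 1.5 in each group. The statistic is 4×(1.5²/1.5) + 2×(3²/12) = 6.0 + 1.5 = 7.5 on 2 df, p = 0.024. Four of the six expected counts are 1.5, which is why an exact version is preferable.

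Ranks hide this difference, and the chi-square test that the plan already names for qualitative data finds it.

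**The case against.** The strongest reply is that the plan never assigns papillary fill to a rank test. Mann-Whitney is tied to the plaque and gingival indices and to most change values. Papillary fill is described as a classification with verbal categories, so it may well belong under qualitative data and chi-square, where the order of levels has no effect. This stands. A reader might infer that the plan counts overgrowth as the best result. The documents do not support that; they show only that the test for this outcome is unnamed.

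It can also be said that the overlap is probably one dropped word, and that a sensible scorer would give a 75% fill the more specific level 3. Both are plausible, but neither can be confirmed from the text, and this wording is the only definition that the documents give. A reader might go further and conclude that the scale cannot be applied at all. That is too strong, because levels 1, 4 and 5 can be scored as written and only the boundary between 2 and 3 fails.

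Finally, the examples were constructed to show the mechanism, and nothing indicates how often level 5 would occur. That also stands: they show what ranks can do, not what happened in this trial.

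**Conclusion.** The overlap is established by the text alone: every papilla with more than half but incomplete fill qualifies for level 2 and level 3. How many scores this affects cannot be known from the documents.

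The analysis point holds in a limited form. The level numbers do not track esthetic quality, and the plan should say which test applies. At 15 per group, ranking the raw number could create an apparent advantage (exact p = 0.035 with equal ideal fill) or conceal a real difference (p = 1.0 with 60% against 100%). Those figures rest on invented counts and one score per patient.

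This is worth correcting, but it concerns one of several esthetic outcomes. A reader might take it to weaken the main comparison. It does not, because gingival margin level, the subject of the title, is measured separately from a stent reference point.

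**What to change.** 1. In section III, define level 2 as filling half or less of the interdental space, with level 1 still reserved for an absent papilla. This meets the boundary that level 3 already states and assigns exactly half.
2. The document is written in the past tense, so scores may already exist. Check recorded 2s and 3s against the corrected wording where the records allow, and report how many change.
3. In section VII, state that papillary fill is qualitative data: tabulate all five levels by group and visit, and compare them as unordered categories, with an exact test where counts are small. Do not use means or ranks of the raw number. If the choice is made after the data have been seen, say so.
4. Optionally, add level 4 against all other levels as a summary. It is unaffected by confusion between levels 2 and 3, but it merges overgrowth with underfill. In Example 1 it compares 12/15 with 12/15 and shows nothing. It should therefore accompany the full table and not replace it.

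The cost is two short text changes and a check of existing scores. The statistical price is some loss of power from ignoring the genuine order of levels 1 to 4.
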